9.7.6. Tolerability

The prevalence and incidence for each AE (Table 3) will be estimated. All prevalence and incidence estimate will be reported as a percent with corresponding 95% CIs.

$$\text{Prevalence} = \left(\frac{\text{Number of patients with an event}}{\text{Total number of patients in the cohort}} \right) \times 100$$

For the incidence analysis, only patients who did not have the event in prior to their index date will be excluded. The length of the washout is dependent on the outcome (see Table 3).

$$\text{Incidence} = \left(\frac{\text{Number of patients with an event who did not have an event at baseline}}{\text{Total number of patients in the cohort}} \right) \times 100$$

Patients will be assessed over two time periods: from the index date until 14 days or 90 days after their last administration of the index medication.

Additionally, the time to infection onset will be assessed using unadjusted Kaplan-Meier methods. The median time to event in days will be reported along with the IQR. The 95% CIs for the median time to event will be calculated using log-log transformation.

Patients will be censored at the earliest of death, the end of continuous closed-claim coverage, the latest data at the time of the specified analysis, or next treatment (CAR-T, BsABs, bendamustine or belantamab).

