Data Sources: This study will use Komodo Health data. The data source is a healthcare technology firm that owns, links, and integrates open and closed-claims databases from over 150 public and private payers/insurers and clearinghouses across the US. The database is closely aligned with the population of the National Health Interview Survey in terms of geography and demographics. This source of insurance claims data encompasses comprehensive, longitudinal records detailing medical procedures, diagnoses, treatments, and associated costs within the healthcare system, as well as patient characteristics and outcomes such as race/ethnicity, zip code, and all-cause mortality records.

The current cut of the data includes over 700,000 patients with MM. The results of this study may be updated as additional data become available for elranatamab.

Study Size: This is a retrospective descriptive cohort study; therefore, sample size calculations are not applicable. As of 24 April 2024, the dataset included 56 patients with a claim for elranatamab.

Data Analysis: Categorical and binary variables will be summarized by the number and percentage of patients in each category. Continuous variables will be described using mean, standard deviation (SD), median, interquartile range (IQR), minimum, and maximum. If applicable, the frequency and percentage of patients with missing data for each variable will be described. Relative Administration Intensity (RAI) will be calculated as the ratio of the actual number of administrations during each time period divided by the expected number of administrations based on the label for the treatment. All-cause HCRU and MM-related HCRU will be measured as the mean, SD, median, IQR, minimum, and maximum of the total number of IP, OP, ED, and pharmacy claims that occurred over the follow-up period and in the 180-day baseline period. Given the variable follow-up time available for each patient, HCRU and costs will be reported per-patient-per-month (PPPM). The prevalence and incidence, as well as the associated 95% confidence intervals (CI) for each AE, will be estimated. Kaplan-Meier methods will be used to estimate the median time to event, including 95% CIs for TTNT/D, TTD, and OS. All analyses will be repeated in an exploratory cohort of patients receiving teclistamab.

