		PJP Hepatitis C Hepatitis B Other infectious hepatitis Helicobacter pylori Candida esophagitis Urinary tract infection	
Effectiveness			
Exploratory Obj 2	OS	Time (in months) from index date until date of death (continuous)	Index date until censor See Section 9.7.7 for censoring criteria
Exploratory Obj 2	TTNT/D	Time (in months) from index date until the date of the next treatment (CAR-T, BsABs, bendamustine or belantamab) or death (continuous)	Index date until censor See Section 9.7.7 for censoring criteria

1. Variable will be measured as incident and prevalent. Incident cases have 30-day washout period applied
2. Variable will be measured as incident and prevalent. Incident cases have 60-day washout period applied
3. Variable will be measured as incident and prevalent. Incident cases have 14-day washout period applied

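### Section 9.7.6 inverts the exclusion rule for AE incidence and divides by the whole cohort, so incidence is understated for any AE that some patients had in its washout

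*Protocol*

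**What the plan says.** Section 9.7.6 plans a prevalence and an incidence for the AEs in Table 3, each as a percentage with a 95% CI.

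- Exclusion rule for incidence: "For the incidence analysis, only patients who did not have the event in prior to their index date will be excluded".
- Incidence numerator: "Number of patients with an event who did not have an event at baseline".
- Incidence denominator: "Total number of patients in the cohort". The prevalence formula just above it uses the same words.
- Washout: its length depends on the AE. The Table 3 footnotes (Section 9.3) give three lengths: "Incident cases have 30-day washout period applied" (CRS, ICANS, cytopenias and others), "Incident cases have 60-day washout period applied" (renal failure and most infections) and "Incident cases have 14-day washout period applied" (pyrexia, fatigue, arthralgia and others). The sinusitis and bronchitis rows carry no footnote.

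Section 9.7 uses the word cohort for the elranatamab and teclistamab treatment groups, which are reported separately. Section 9.8 commits the analysts to follow the protocol strictly.

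**The concern.** An incidence proportion needs a numerator of new cases and a denominator of the people who could become new cases. Section 9.7.6 departs from this twice. Its exclusion sentence removes the people who could become new cases. Its formula excludes nobody from the denominator, although patients with a washout event are barred from the numerator. Sentence and formula cannot both be followed.

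The error in the formula can only lower an incidence, never raise it, so the drug looks better tolerated than the data show. Its size changes with the AE, with the washout length and with the cohort. Even purely descriptive percentages then lose a common meaning across AEs, or when the elranatamab and teclistamab tables are laid side by side. Section 7 designates the study a post-authorisation safety study. Under Section 9.8, a quality check against the protocol would confirm the printed denominator rather than catch it.

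**Working it through.** The protocol states no incidence value, so there is no planned figure to reproduce. The check is algebra followed by an illustration.

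**Inputs.** N is the number of patients in the treatment cohort. B is the number with the event in the AE-specific washout, and b = B/N. x is the number of new events among the N − B patients at risk. Neither B nor b is in the documents, so b is an assumption, ranged from 0 to 50%. For illustration N = 56, the count of patients with an elranatamab claim in Section 9.5 (dated 24 April 2024 in the abstract). That count precedes the eligibility criteria and all data refreshes.

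**Reading 1: the sentence taken literally.** Patients without a prior event are removed, so only the B patients with one remain. The numerator requires no event at baseline, so it is 0. Every incidence is 0%, or undefined if the denominator is also restricted and B = 0.

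**Reading 2: the sentence treated as a slip, the formula used as printed.**

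- Printed incidence = x / N
- At-risk incidence = x / (N − B)
- Ratio, printed to at-risk = (N − B) / N = 1 − b

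The ratio is 1.00 at b = 0, 0.95 at 5%, 0.90 at 10%, 0.75 at 25% and 0.50 at 50%. The correction factor 1/(1 − b) is 1.00, 1.05, 1.11, 1.33 and 2.00.

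With N = 56, an at-risk incidence near 40% and exact (Clopper-Pearson) 95% CIs:

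| B (b) | x | Printed, x/56 | At risk, x/(56 − B) | Ratio |
|---|---|---|---|---|
| 0 (0%) | 22 | 39.3% (26.5–53.2) | 22/56 = 39.3% (26.5–53.2) | 1.000 |
| 3 (5.4%) | 21 | 37.5% (24.9–51.5) | 21/53 = 39.6% (26.5–54.0) | 0.946 |
| 6 (10.7%) | 20 | 35.7% (23.4–49.6) | 20/50 = 40.0% (26.4–54.8) | 0.893 |
| 14 (25.0%) | 17 | 30.4% (18.8–44.1) | 17/42 = 40.5% (25.6–56.7) | 0.750 |
| 28 (50.0%) | 11 | 19.6% (10.2–32.4) | 11/28 = 39.3% (21.5–59.4) | 0.500 |

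The two columns divide the same events by different denominators. They are not independent estimates, so overlap of their intervals is not a test of anything. At a lower risk and small b the gap is modest: 15/50 = 30.0% against 15/56 = 26.8%, about 3 percentage points.

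**Reading 3: the sentence corrected, and cohort read as the patients left after exclusion.** The denominator becomes N − B and there is no bias. The text does not say this, and Section 9.7 uses the word for the treatment group.

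**Is b likely to be above zero?** Section 7 describes myeloma as marked by low blood counts, renal failure and susceptibility to infection. Table 2 lists neutropenia, renal failure, peripheral neuropathy and infections as baseline characteristics. Some washout cases are therefore to be expected for several of the AEs, though the documents do not say how many.

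**The case against.** The best defence is that the intent is plain. The sentence is visibly garbled, and the reference to a washout, the numerator and the Table 3 footnotes all point to the usual rule. An analyst would probably reverse the sentence, exclude first, and then take the formula over whoever is left, which gives the right answer. This makes the literal result of 0% unlikely in practice. It does not rescue the denominator: the words are those of the prevalence formula, where they must mean everyone, and nothing signals a different meaning a few lines later.

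Scope also counts in the plan's favour. Safety is an exploratory objective, and Section 9.7 rules out formal comparisons between groups. Incidence is not the only safety measure either: the prevalence formula is correct with a whole-cohort denominator, and time to infection onset is estimated separately. A reader might infer that the whole safety objective fails; it does not.

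A reader might also fault the plan for giving crude AE percentages when the abstract says of resource use: "Given the variable follow-up time available for each patient, HCRU and costs will be reported per-patient-per-month (PPPM". Or a reader might fault it for censoring at death in the time-to-infection analysis. These are choices of estimator. A proportion over a defined window, to 14 or 90 days after the last administration, is an ordinary descriptive measure, and the protocol does not contradict itself there.

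**Conclusion.** Two statements in Section 9.7.6 are wrong as written: the exclusion sentence is inverted, and the incidence denominator is the whole cohort rather than the patients at risk. With the formula as printed, incidence is understated by the factor 1 − b for every AE with any washout-period cases.

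It would be tempting to conclude that every reported AE incidence is too low. The documents do not support that. Where nobody had the event in the washout, the printed formula is right; CRS and ICANS may come close to this with a 30-day window, although no baseline rates are given. For sinusitis and bronchitis no washout is marked, so it is unclear whether an incidence is planned at all. Large distortions such as a halving require b = 50%, which is an assumption with no support in the text. The direction of the error and the factor 1 − b do not depend on N = 56 or on any assumed b; the size for a given AE does.

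**What to change.** Make two edits in Section 9.7.6:

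1. Reverse the exclusion sentence, so that patients **with** the event in the AE-specific washout are excluded from the incidence analysis of that AE.
2. Change the incidence denominator to the number of patients in the cohort without the event in that washout. Leave the prevalence formula unchanged.

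Then check which denominator was used in results already produced. Section 6 schedules full results and two refreshes before the date of this protocol version. Rerun any AE incidence tables that used the printed formula.

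The cost is one sentence, one denominator and a rerun of those tables. The downside is somewhat wider CIs from the smaller denominator: in the example with B = 14, the interval goes from 18.8–44.1% to 25.6–56.7%, a width of 31.1 instead of 25.3 points.

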Exploratory Obj 1	Hepatitis C ²	Medical claim with an ICD-10 code in the IP, non-IP or pharmacy setting for hepatitis C (dichotomous)	Index date to end of follow-up, where follow-up will be based on last dose of elranatamab (eg, 14 days after last recorded dose or 90 days after last recorded dose). See Section 9.7.6 for censoring criteria
Exploratory Obj 1	Hepatitis B ²	Medical claim with an ICD-10 code in the IP, non-IP or pharmacy setting for hepatitis B (dichotomous)	Index date to end of follow-up, where follow-up will be based on last dose of elranatamab (eg., 14 days after last recorded dose or 90 days after last recorded dose). See Section 9.7.6 for censoring criteria
Exploratory Obj 1	Other infectious hepatitis ²	Medical claim with an ICD-10 code in the IP, non-IP or pharmacy setting for other infectious hepatitis (dichotomous)	Index date to end of follow-up, where follow-up will be based on last dose of elranatamab (eg., 14 days after last recorded dose or 90 days after last recorded dose). See Section 9.7.6 for censoring criteria
Exploratory Obj 1	Helicobacter pylori ²	Medical claim with an ICD-10 code in the IP, non-IP or pharmacy setting for helicobacter pylori (dichotomous)	Index date to end of follow-up, where follow-up will be based on last dose of elranatamab (eg, 14 days after last

			recorded dose or 90 days after last recorded dose). See Section 9.7.6 for censoring criteria
Exploratory Obj 1	Candida esophagitis ²	Medical claim with an ICD-10 code in the IP, non-IP or pharmacy setting for candida esophagitis (dichotomous)	Index date to end of follow-up, where follow-up will be based on last dose of elranatamab (eg, 14 days after last recorded dose or 90 days after last recorded dose). See Section 9.7.6 for censoring criteria
Exploratory Obj 1	Urinary tract infection ²	Medical claim with an ICD-10 code in the IP, non-IP or pharmacy setting for a urinary tract infection (dichotomous)	Index date to end of follow-up, where follow-up will be based on last dose of elranatamab (eg, 14 days after last recorded dose or 90 days after last recorded dose). See Section 9.7.6 for censoring criteria
Exploratory Obj 1	Time to infection onset	Time in days from index date to first infection for the following infections: COVID-19 Sinusitis Bronchitis Adenoviral pneumonia Cytomegaloviral pneumonitis Pneumonia Sepsis Cytomegaloviral infection	Index date until censor See Section 9.7.6 for censoring criteria

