9.4. Data Sources

This study will be conducted using Komodo Health's Healthcare Map™. The data source is a healthcare technology firm owning, linking, and integrating both open and closed-claims databases from over 150 public and private payers/insurers as well as clearinghouses across the US. The database linkage uses Datavant's encryption and tokenization technology. The data covers more than 330 million individuals including both current (alive) and historical (deceased during the time of study) patients. The database is closely aligned with the National Health Interview Survey population in terms of geography and demographics. This source of insurance claims data encompasses comprehensive, longitudinal records detailing medical procedures, diagnoses, treatments, and associated costs within the healthcare system, as well as patient characteristics and outcomes such as race/ethnicity, zip code, and all-cause mortality records. In this iteration of the Komodo Healthcare Map, only patients with at least one ICD diagnosis code for MM are included in the database.

Mortality records in the data source are obtained from government public records, private claims, and obituaries. For Health Insurance Portability and Accountability Act compliance reasons, mortality is truncated to the year/month of death (YYYY-MM-01). Multiple sources of data are then evaluated, and death dates within 30 days of each other are deduplicated. If multiple sources report different death dates for the same person, then the earlier date is taken.

In order to impute costs, Komodo Heath utilizes the data provided to them by their data sources as well as from as well as publicly available Centers for Medicare & Medicaid Services Medicare fee-for-service pricing tools and methodologies.

This study involved secondary research that utilized de-identified data licensed from a third party, Komodo, in compliance with 45 Code of Federal Regulations 164.514(a)-(c).

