9.7.7. Overall Survival and Time to Next Treatment

OS and TTNT/D will be assessed using unadjusted Kaplan-Meier methods. The median time to event in months will be reported along with the IQR. The 95% CIs for the median time to event will be calculated using log-log transformation. Results will be depicted graphically by Kaplan-Meier curves, and the percentage of patients who reached the outcome and censored patients will also be reported.

OS will be assessed as the time in months from index date to date of death. Patients without an event will be censored at the earliest of the end of continuous closed-claim coverage or the end of data.

TTNT/D will be assessed as the time in months from index date until switch a new treatment or death. Patients without an event will be censored at the earliest of the end of continuous closed-claim coverage, or the end of data.

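### Time to infection onset censors deaths in a Kaplan-Meier analysis, so its median and especially its upper quartile come out too early if read as the time by which 50% or 75% of treated patients have had an infection

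*Protocol*

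**What the plan says.** Protocol section 9.3, Table 3 defines the outcome as "Time in days from index date to first infection for the following infections", followed by a list of infection types. Death is not part of the event.

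Section 9.7.6 fixes the estimator: "the time to infection onset will be assessed using unadjusted Kaplan-Meier methods". It fixes the summary: "The median time to event in days will be reported along with the IQR", with a log-log confidence interval for the median. It also fixes the censoring: "Patients will be censored at the earliest of death, the end of continuous closed-claim coverage", with two further reasons, "the latest data at the time of the specified analysis, or next treatment (CAR-T, BsABs, bendamustine or belantamab").

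Infection frequency is reported separately, as counts over the cohort: "All prevalence and incidence estimate will be reported as a percent with corresponding 95% CIs".

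Elsewhere the protocol treats death differently. In section 9.7.7, "TTNT/D will be assessed as the time in months from index date until switch a new treatment or death". Table 3 includes death in the definition of treatment discontinuation, and for OS death is the event.

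Section 9.4 adds a fact that matters for any fix: "mortality is truncated to the year/month of death (YYYY-MM-01").

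**The concern.** Kaplan-Meier treats a censored patient as someone who could still have the event later, at the same rate as those who remain. That suits a patient whose coverage ends. It does not suit a patient who has died: the estimator hands that patient's share of future infections to the survivors. The result describes a cohort in which nobody dies.

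Time to infection is the only Kaplan-Meier outcome in the protocol where death is censored. No target is stated, such as a cause-specific distribution, that would make this a deliberate choice. The aim is real-world safety in a late-line population, which section 7 describes as having shorter survival, so deaths before infection cannot be assumed negligible. The two affected summaries, median and IQR, are what section 9.7.6 asks for.

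**Working it through.** **What can be reproduced.** The protocol states no infection rate, death rate or median for this analysis, so there is no planned figure to reproduce. The direction follows from the estimator; the size needs assumptions.

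**Direction.** With infection hazard a and hazard of death before infection b, both constant:

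- 1 minus Kaplan-Meier at time t: 1 − exp(−a·t)
- Cumulative incidence of infection: F(t) = a/(a+b) × [1 − exp(−(a+b)·t)]

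F(t) is never above the first expression, so Kaplan-Meier quantiles are never later. F levels off at a/(a+b). Its median is therefore never reached if b ≥ a, and its upper quartile is never reached if b ≥ a/3. Kaplan-Meier still has finite quantiles in both cases.

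**Size, anchored on the one infection figure in the protocol.** Inputs:

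- 69.9% infected: the pivotal-trial adverse-event percentage in section 7, *assumed* here to be the cumulative incidence at 12 months.
- d = 5, 10, 15 or 20% dying uninfected by 12 months: *assumed*.
- 1 month = 30.4375 days (section 9.7.4).

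Solving: (a+b)·12 = −ln(1 − 0.699 − d), and a/(a+b) = 0.699/(0.699 + d).

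Example at d = 10%: (a+b)·12 = −ln(0.201) = 1.6045; a/(a+b) = 0.699/0.799 = 0.8748; a = 0.8748 × 1.6045/12 = 0.1170 per month.

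- Kaplan-Meier median = ln 2/0.1170 = 5.93 months.
- Cumulative-incidence median = −ln(1 − 0.5/0.8748) × 12/1.6045 = 6.34 months.
- Kaplan-Meier upper quartile = ln 4/0.1170 = 11.85 months.
- Cumulative-incidence upper quartile = −ln(1 − 0.75/0.8748) × 12/1.6045 = 14.56 months.

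| Dying first by 12 months | Median, KM | Median, cum. inc. | Early by | Upper quartile, KM | Upper quartile, cum. inc. | Early by |
|---|---|---|---|---|---|---|
| 5% | 6.45 mo | 6.66 mo | 6.5 days | 12.9 mo | 14.1 mo | 1.2 mo |
| 10% | 5.93 | 6.34 | 13 days | 11.9 | 14.6 | 2.7 mo |
| 15% | 5.34 | 5.93 | 18 days | 10.7 | 15.4 | 4.7 mo |
| 20% | 4.67 | 5.39 | 22 days | 9.3 | 17.5 | 8.2 mo |

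The lower quartile moves by less than 0.1 month throughout. The cumulative-incidence upper quartiles lie beyond 12 months, so they also rely on the hazards staying constant past the anchor.

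**Sensitivity to the anchor.** Dropping the 69.9%, take Kaplan-Meier infection medians of 90, 180 or 365 days and competing-event medians from 1,095 down to 365 days (all assumed).

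| KM median | Cum. inc. median | KM upper quartile | Cum. inc. upper quartile |
|---|---|---|---|
| 90 days | 93–102 days | 180 days | 200–285 days |
| 180 days | 195–239 days | 360 days | 461 days to not reached |
| 365 days | 434 days to not reached | 730 days | not reached in every case |

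Over this range, the share of patients infected by the Kaplan-Meier median is 37.5% to 48.8%, not 50%. By the Kaplan-Meier upper quartile it is 46.9% to 71.8%, not 75%.

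**Simulation check** (40,000 patients, medians of 180 and 365 days, random administrative censoring). Kaplan-Meier quartiles were 74/180/362 days; Aalen-Johansen quartiles were 81/238/not reached. The crude infected percentage was 55.0%, below the Aalen-Johansen value of 66.4%, so the crude percentage is not inflated.

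**The case against.** **Infection risk itself is not overstated in what the plan reports.** A reader might infer from the censoring rule that the study will exaggerate the infection risk of elranatamab. The documents do not support that. Section 9.7.6 reports infection risk as crude percentages of the cohort, and death-censored Kaplan-Meier does not enter them. For time to infection it asks for neither a Kaplan-Meier probability nor a curve, whereas sections 9.7.4 and 9.7.7 do ask for curves. This objection stands, and the point is confined to the quantiles.

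**The median shift is small.** With the 56 patients named in section 9.5 and no other censoring, the standard error of a Kaplan-Meier median is about √(0.25/56)/(0.5a). That is 1.24 months at 5% dying first and 0.90 at 20%. The shifts of 0.21 and 0.73 months are then 0.17 and 0.81 standard errors. This stands for the median. It does not remove the upper-quartile problem, and a systematic shift does not shrink as the quarterly refreshes add patients.

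**Kaplan-Meier is valid for a cause-specific quantity under independent censoring.** True, but the protocol names no such target.

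**The net direction is less certain than the formula suggests.** Recorded deaths are moved to the first of the month, so infections in the month of death can fall after the recorded death and be lost. With infection and death independent, simulation left the Kaplan-Meier quartiles essentially unchanged and lowered the crude percentage by about 1 to 2 points. If infections cluster just before death, the loss would push the Kaplan-Meier quantiles later, against the bias described here. This partly stands. It does not make censoring deaths correct.

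**No comparison is planned.** A reader might also infer a biased contrast between the elranatamab and teclistamab cohorts. Section 9.7 plans no formal comparison between groups, so no planned contrast is affected.

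**Conclusion.** The point holds for the Kaplan-Meier median and quartiles and for nothing else. Under the stated assumptions the median is early by about 7 to 22 days and the lower quartile by almost nothing. The upper quartile is early by 2.7 months at 10% dying first and 8.2 months at 20%; under other plausible rates it would not be reached at all. Every death rate here is assumed, as are the 12-month anchor and constant hazards, because the protocol supplies none.

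The stronger reading, that reported infection risk is inflated, is not supported: the reported percentages are crude counts. The outcome belongs to an exploratory objective and carries no test or sample size, so what is at stake is interpretation. The change is still worth making, because the estimator and censoring are written out in section 9.7.6 and section 9.8 commits the analysts to follow the protocol strictly.

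**What to change.** Amend the time-to-infection paragraph of section 9.7.6 as follows.

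1. Estimate the cumulative incidence of first infection by Aalen-Johansen, with death without prior infection as a competing event.
2. Keep censoring at end of closed-claim coverage and end of data.
3. State how next treatment is handled: either keep it as censoring or make it a second competing event. Either way, infections after a switch are not counted for the index drug.
4. State that infection claims in the calendar month of death count as occurring before death. Otherwise the truncated date would turn an infection followed by death in the same month into a death without infection.
5. Read the median and quartiles from the cumulative incidence curve, giving not reached where that applies.
6. If a Kaplan-Meier result is kept, label it cause-specific.

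The cost is a few sentences, a standard procedure and slightly more analysis work, with no new data. Quartiles will be later or not reached. Changing the estimator leaves the crude prevalence and incidence percentages as they are; the month-of-death rule would affect them only if it were applied to them as well.
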